4.1.4. Dose Escalation Committee

The Dose Escalation Committee (DEC) will be established by GSK to monitor intervention-emergent data on an ongoing basis throughout study conduct for the purpose of ensuring the continued safety of participants enrolled in this study. The DEC will be chaired by the GSK medical monitor and membership will include a GSK scientist, GSK pharmacovigilance physician, GSK statistician, GSK pharmacologist, along with additional GSK staff as appropriate and all participating investigators.

In Part 1, the DEC will review relevant safety, PK, and PD data generated immediately after all participants treated in the same dose cohort have passed the DLT period, as defined in the Dose Escalation Plan. Although the escalation of the GSK3368715 dose will be guided by the N-CRM, the DEC can override this recommendation.

In Part 2, the members from the DEC will continue to routinely assess cumulative safety data as a safety evaluation team. This team may decide to stop further enrolment if intervention-emergent toxicity is determined to result in an unfavourable change in participant risk/benefit.

In addition, throughout the conduct of the study the DEC may decide to:

1. Modify the dose escalation of GSK3368715 proposed by the N-CRM based on clinical judgement. *Note:* GSK3368715 dose steps will not exceed 50 mg dose increments under protocol amendment 03.
2. Investigate alternative dosing regimens
3. Modify the timing, frequency, and/or type of safety assessments performed during study conduct
4. Request intervention of additional participants at previously completed dose levels for the purpose of obtaining additional safety, PK, PD, metabolite, or biomarker data (i.e. PK/PD/Metabolite/Biomarker-Cohort).
5. Recommend intra-participant dose escalation allowing participants to be moved from a lower to a higher GSK3368715 dose, not exceeding the MTD if the DEC has declared the next dose cohort as safe
6. Decide on intervention beyond initial evidence of disease progression in participants who receive clinical benefit (i.e., stable Eastern Cooperative Oncology Group or ECOG performance status and no clinical symptoms indicative of rapid disease progression)
7. Increase the size of an expansion cohort or recommend to add additional expansion cohorts to further characterize the safety and efficacy profile of GSK3368715
8. Halt enrolment into any cohorts as deemed appropriate based on emerging clinical data at any time during the trial.

During Part 1 of the study, the DEC will meet at least after each dose cohort is fully recruited and all participants have completed the DLT evaluation period. The schedule of dose escalation meetings will depend on the frequency of DLT and when an RP2D is determined. During Part 2 of the study, the DEC will meet approximately after every 10 participants in each expansion cohort have been on study for ≥ 2 cycles.

Documentation of DEC meeting outcomes will be maintained by GSK. Decisions with potential impact on the safety of study participants (i.e. unfavourable change in risk/benefit assessment) will be promptly communicated to regulatory authorities and study sites as appropriate.

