Thromboembolic Risk	A higher than expected incidence of venous thromboembolism was observed in the first 19 participants treated on clinical study 207675.	
 • Change in inclusion/exclusion criteria, to exclude participants at high risk of VTE. • Extended monitoring time for VTE events to clear dose prior to dose escalation. • Include cohort stopping rules for VTE • Resume enrollment under protocol amendment 03 at reduced dose of 100 mg po daily • Limit dose escalation to 50 mg increments.
Study procedures		
Biopsy	A tissue biopsy is required in PK/PD cohorts to evaluate tumor expression of the biomarkers pathway. Risks associated with a tumor biopsy depend upon the location and type of biopsy performed. Pain, infection, bleeding may occur after the procedure. Additional risks depending on the location of the biopsy may include pneumothorax, pneumonia, injury to surrounding nerves or organs, hospitalization, and, rarely, death.	
 • Participants will be informed of the specific risks associated with the biopsy to be performed through the ICF. Participants at increased risk or not well suited to undergo a biopsy should not be enrolled in a cohort that requires a fresh biopsy. Participants will be treated according to local practice.

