 - Upon re-initiation of enrolment under Protocol Amendment 3, details of a VTE meeting the DLT criteria are given in Section 4.1.3 and in Table 6.
- Upon re-initiation of enrolment under Protocol Amendment 3 at 100mg , dose escalation steps will be considered in maximal steps of 50 mg, depending on the pharmacodynamic effects and the safety profile observed in previous cohorts, taking into consideration the updated DLT criteria (see Table 6).
- *Note:* GSK3368715 dose de-escalation is also possible using this method.

An updated posterior estimate of the dose-toxicity curve will also be provided at the time of the dose-escalation meeting. Further details about the N-CRM approach are provided in Section 9. Although the N-CRM will be used to recommend the next dosing level, the DEC (i) will review all available data, including safety, PK and PD data from current and prior cohorts, (ii) can halt or reduce the GSK3368715 dose based on clinical judgement at any time during the trial, and (iii) can recommend alternative schedule(s) if emerging data suggest that continuous daily dosing will result in excessive toxicity or limited efficacy (Section 4.1.4). *Note:* if an alternative schedule is evaluated, the starting dose at the time of a schedule change will be the dose for which the target toxicity level was not exceeded using once daily dosing schedule.

Dose Schedule: GSK3368715 will be dosed initially orally (po) Based on emerging safety-, PK-, and PD- data, the DEC may recommend to evaluate alternative dosing schedule(s). The starting dose for an alternative dosing schedule will not exceed the highest GSK3368715 dose declared safe by the DEC at the time of the proposed schedule change.

During dose escalation, the first dose will be staggered by at least 24 hours between the participants enrolled within a cohort. This staggered dosing start is not required for participants enrolling at previously cleared doses.

PK/PD/Metabolite/Biomarker-Cohort: At GSK3368715 dose levels near to the expected RP2D, the DEC may recommend to expand a cohort(s) to up to 12 participants for additional PK- and PD-, metabolite- and/or biomarker-sample collection.

Under protocol amendment 03, a 100mg PK/PD cohort will be opened on resuming enrolment, and a 50mg PK/PD cohort may be opened in parallel. An additional PK/PD cohort may be opened later at a different dose level. The total maximal number of participants enrolled on PK/PD cohorts will be approximately 30.

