4.1.3. Dose-Limiting Toxicity

All toxicities will be graded using National Cancer Institute – Common Toxicity Criteria for Adverse Events (NCI-CTCAE), version 5.

An AE is considered to be a dose-limiting toxicity (DLT) if the event is considered by the investigator to be clinically relevant and attributed (definitely, probably or possibly) to the study intervention during the first 21 days of intervention and meets at least one of the criteria listed in [Table 6](#).

In addition, there are clear VTE DLT criteria:

- Upon re-initiation of enrolment under Protocol Amendment 3, any cohort in Part 1 with two (2) grade 2 venous thromboembolism (VTE) that requires systemic anticoagulation or \geq grade 3 VTE in up to 6 participants will be considered not cleared and enrolment at this dose level and higher dose levels will be permanently stopped.
- Upon re-initiation of enrolment under Protocol Amendment 3, any cohort in Part 1 with ≥ 3 grade 2 venous thromboembolism (VTE) that requires systemic anticoagulation or Grade ≥ 3 VTEs out of up to 10 participants will be considered not cleared and enrolment at this dose level and higher dose levels will be permanently stopped.
- Upon re-initiation of enrolment under Protocol Amendment 3 at 100mg, dose escalation steps will be considered in maximal steps of 50 mg depending on the pharmacodynamic effects and the safety profile observed in previous cohorts, taking into consideration the updated DLT criteria (see [Table 6](#)).
- Grade 2 venous thromboembolism (VTE) that requires systemic anticoagulation or \geq grade 3 VTE, regardless of investigator assessed causality, will be considered a DLT during the first 8 (± 1) weeks or until study discontinuation (e.g., disease progression), whichever occurs sooner.
- An end of treatment CT image is required if the participant withdraws before the end of the VTE DLT observation period ([Table 6](#)).

If an AE is considered related to the underlying disease it is not defined as a DLT.

Table 6 Dose-Limiting Toxicity Criteria

DLT criteria for Non-hematologic Toxicity	
AST or ALT	
 • Grade 3 • Grade 4 • ALT \geq 5xULN • ALT \geq 3xULN persists for \geq 4 weeks • ALT \geq 3xULN and bilirubin \geq 2xULN (>35% direct bilirubin) • ALT \geq 3xULN and INR >1.5, if INR measured • ALT \geq 3xULN associated with symptoms (new or worsening) believed to be related to liver injury or hypersensitivity

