### 3. PLANNED ANALYSES

#### 3.1. Interim Analyses

In Part 1, dose escalation meetings will be held to discuss dose escalation decisions after all patients in each dose cohort complete the DLT evaluation period of the first 21 days of intervention. Once all subjects in the DLT evaluation cohort (approx. 30 in total) have completed the first post baseline disease assessment, progressed or permanently discontinued from study treatment, a RP2D analysis will be conducted.

The Dose Escalation Committee (DEC) evaluated the DL100mg cohort and deemed it safe, but upon review of the cumulative safety, efficacy, PK and PD data, GSK decided that no further enrolment will take place on the study. As a result, all analyses corresponding to Part 2, as well as the Exploratory Objectives for both Part 1 and Part 2, will not be performed. However, all other Part 1 analyses will be performed.

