### 5.2. Reporting Conventions

- Unless otherwise specified, the denominator in percentage calculation at each scheduled visit will be based on the number of subjects with a non-missing value at each particular visit.
- All data are reported according to the dose/regimen initially received by the subject.
- Data will be listed by treatment group, site ID, and subject.
- Planned times relative to investigational product dosing will be used in all summary tables and figures.
- Actual, rather than planned, sampling times will be used in the derivation of PK parameters and in the individual concentration-time plots. Planned times will be used in the descriptive summaries and in mean and median plots. Listings of PK concentration-time data will be done by actual sampling times relative to dosing time.
- Unless stated otherwise, descriptive summaries will include n, mean, standard deviation (SD), median, minimum and maximum for continuous variables and n and percent for categorical variables. Display minimum and maximum in the same precision as data was collected, mean and median using 1 additional decimal place, and SD using 2 additional decimal places.
- This is a multicenter study. Data from all study sites will be integrated and no controlling for site-effect will be considered in the statistical analyses.
- Analyses are to be performed using the SAS System, Version 9.4 or higher. Programs will be imported into HARP and the final output will be produced by running drivers in HARP. Some graphics may be produced using the TSCG (Tibco Spotfire Clinical Graphics) - comprising of S-Plus (R) 7.0.6 or higher.
- Deviations from the analyses in the RAP will be identified in the final CSR.

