| 3.17.                               | All Treated       | EG2                             | Summary of Change from Baseline in ECG Values by Visit                        | IDSL                     | SAC                |
| Vital Signs                  |                   |                                 |   |                          |                    |
| 3.18.                               | All Treated       | VS1                             | Summary of Change from Baseline in Vital Signs                                | ICH E3                   | SAC                |
| Dose Modifications           |                   |                                 |   |                          |                    |
| 3.19.                               | All Treated       | ODMOD1                          | Summary of Dose Reductions of GSK3368715                                      | ICH E3                   | SAC                |
| 3.20.                               | All Treated       | ODMOD2                          | Summary of Dose Interruptions of GSK3368715                                   | ICH E3                   | SAC                |
| 3.21.                               | All Treated       | ODMOD8                          | Summary of Dose Escalations of GSK3368715                                     | If applicable.           | SAC                |
| Dose Limiting Toxicity (DLT) |                   |                                 |   |                          |                    |
| 3.22.                               | All Treated       | DL1                             | Summary of Dose-Limiting Toxicities during the Determinative Period           | ICH E3                   | SAC                |

| Safety: Tables            |             |                      |  |                   |             |
|---------------------------|-------------|----------------------|--|-------------------|-------------|
| No.                       | Population  | IDSL / Example Shell | Title  | Programming Notes | Deliverable |
| Performance Status |             |                      |  |                   |             |
| 3.23.                     | All Treated | PS1A                 | Summary of ECOG Performance Status                         | ICH E3            | SAC         |

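### Protocol 4.1.4 item 5 allows a dose increase inside the 8-week VTE DLT window; SAP 5.2 would then report a VTE that began on the higher dose under the starting dose.

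*Protocol*

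**What the plan says.** - **Permission to move.** Protocol 4.1.4, item 5, is one of the decisions open to the DEC. It may recommend that participants be "moved from a lower to a higher GSK3368715 dose, not exceeding the MTD if the DEC has declared the next dose cohort as safe". Those are the only two conditions; time already spent on the first dose is not one.
- **VTE window.** Protocol 4.1.3 and Table 6 count a Grade 2 VTE needing systemic anticoagulation, or any VTE of Grade 3 or higher, as a DLT. Under 4.1.3 this holds whatever the investigator's view of causality. The window is the first 8 (±1) "weeks or until study discontinuation (e.g., disease progression), whichever occurs sooner". A dose change does not end it, and dose at onset is not mentioned.
- **Clearance.** Protocol 2.3.1 lists as a mitigation "Extended monitoring time for VTE events to clear dose prior to dose escalation". SAP 3.1 instead places dose-escalation meetings "after all patients in each dose cohort complete the DLT evaluation period of the first 21 days of intervention".
- **Enrolment at a lower dose.** Protocol 4.1.1 says "a 100mg PK/PD cohort will be opened on resuming enrolment, and a 50mg PK/PD cohort may be opened in parallel". Protocol 4.1.4, item 4, lets the DEC "Request intervention of additional participants at previously completed dose levels".
- **Reporting.** SAP 5.2: "All data are reported according to the dose/regimen initially received by the subject". No exception is made for DLTs. SAP Table 3.22 is titled "Summary of Dose-Limiting Toxicities during the Determinative Period", and Listing 22 carries the same limit. The SAP does not define that period.

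**The concern.** DLT incidence is a Part 1 primary endpoint, and Protocol 9.6.2.2 has DLTs summarised by dose cohort. Amendment 3 lengthened the VTE window because of the thromboembolic events seen in the first 19 participants. The longer the window, the more room there is for a dose change inside it.

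Suppose a participant starts on 50 mg, is raised to 100 mg in Week 4 and has a qualifying VTE in Week 7. The event is a DLT under 4.1.3, and SAP 5.2 puts it in the 50 mg column. VTE then looks more frequent at 50 mg and less frequent at 100 mg than it was. Protocol 2.3.1 protects the step from one cohort to the next, but item 5 does not carry that protection to the individual participant.

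**Working it through.** **1. Can an in-window move arise?**

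- *Sequential cohorts, each cleared at 8 weeks.* By the time the higher cohort is declared safe, everyone in the lower cohort is past day 56. There is no gap.
- *Parallel 50 mg PK/PD cohort (4.1.1).* A 50 mg participant can be mid-window when 100 mg is declared safe. This is the clearest route.
- *Participants added at a completed dose (item 4).* If a higher dose is already cleared, both of item 5's conditions can be met from the first day.

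**2. Where would the VTE be reported?** By 4.1.3 it is a DLT if it falls within 8 (±1) weeks of the start. By SAP 5.2 it goes under the starting dose. It reaches Table 3.22 and Listing 22 only if the determinative period includes the VTE window. If that period is 21 days, a VTE in Weeks 4–8 is not in those displays at all.

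**3. The plan's own figures.** Protocol 9.2.1.1 stops a cohort at 2 or more VTEs among the first 6, or 3 or more among 7–10. With X6 and X4 the counts in the first 6 and the next 4:

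P(pass) = P(X6=0)·P(X4≤2) + P(X6=1)·P(X4≤1)

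The stopping probability 1 − P(pass) is 3.64% at a true risk of 5%, 42.3% at 20% and 69.5% at 30%. Table 8 gives 3.8, 42.1 and 69.5, so the rule is reproduced. P(pass) is 0.577 at 20% and 0.305 at 30%.

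**4. Illustration.** These are assumptions, not document figures: 8-week VTE risk of 5% at 50 mg and 20% or 30% at 100 mg; constant hazard within each dose; 2 or 4 of 10 participants moved; 100 mg first passing its own VTE rule in 10 participants.

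Let f be the share of the 8 weeks spent at 50 mg. The chance that one mover has a VTE on 100 mg inside the window is

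q = 0.95^f × [1 − (1 − p100)^(1−f)]

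and the chance that 100 mg passes and at least one of m movers has such a VTE is P(pass) × [1 − (1 − q)^m].

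Worked case, move at Week 4 (f = 0.5), p100 = 20%: q = 0.9747 × (1 − 0.8944) = 0.103. For m = 2, 1 − 0.897² = 0.195, and 0.577 × 0.195 = 11.3%.

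| Move at | p100 | q | 2 moved | 4 moved |
|---|---|---|---|---|
| Week 4 (f = 0.5) | 20% | 0.103 | 11.3% | 20.3% |
| Week 4 | 30% | 0.159 | 8.9% | 15.3% |
| Week 6 (f = 0.75) | 20% | 0.052 | 5.9% | 11.1% |
| Week 6 | 30% | 0.082 | 4.8% | 8.8% |

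The ranges are about 9–20% for Week 4 and 5–11% for Week 6. The figures are lower at 30% than at 20% because 100 mg is then less likely to pass and so to open the way for a move.

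**The case against.** **The gap may be closed elsewhere.** Protocol 4.1.4 refers to the Dose Escalation Plan for the DLT period, and that plan is not supplied. Item 5 is a discretionary power of a committee that includes a pharmacovigilance physician and a statistician. This stands: silence in item 5 shows that the protocol does not bar an in-window move, not that the trial would have made one.

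**The routes are narrow.** The parallel 50 mg cohort was optional. SAP 2.1 says that the DEC deemed 100 mg safe and that the sponsor then ended enrolment, so no one can now be added under item 4. The SAP's PK tables split only 100 mg by cohort, which would fit with no separate 50 mg PK/PD cohort having been filled. SAP Table 3.21 on dose escalations is marked as applying only if needed. All of this stands and keeps the point minor.

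**A third route is tempting but weak.** If dose clearance followed the 21 days of SAP 3.1, a second cohort could clear at day 21 + 21 = 42, leaving 14 of 56 days on the higher dose. But the SAP is a reporting plan, its own design summary carries the 8-week VTE DLT, and Protocol 2.3.1 points to longer monitoring before clearance. I do not rely on this route.

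**A table that follows its declared convention is not in error.** That is fair, and dose at onset can be recovered by reading the exposure and DLT listings together. The summary by dose would still mislead a reader who took the column as the dose at the event.

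**Dose at onset is itself uncertain.** The first scheduled on-treatment chest CT is Week 9 Day 1. A silent clot that formed on 50 mg could carry the scan date and look like a 100 mg event. This stands, and it is why the fix does not move events between columns.

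**Conclusion.** The point holds as a minor one. Item 5 allows a dose increase inside the VTE DLT window, and SAP 5.2 would report a later in-window VTE under the starting dose. For Table 3.22 and Listing 22 this depends on the determinative period covering the 8 weeks.

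The 9–20% and 5–11% figures are conditional on in-window moves and rest on assumed risks and an assumed number of movers. They are not the trial's overall risk of a misplaced event, because the chance of any such move cannot be estimated from the documents.

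A reader might infer two stronger things. The first is that the Part 1 DLT results are distorted; nothing shows that any participant was moved inside the window. The second is that such a VTE would push the lower dose towards closure under the 4.1.3 stopping rule. SAP 5.2 is a reporting convention, and neither document says which dose the event would carry in the live count or in the N-CRM. I therefore give no closure figure.

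**What to change.** 1. **Protocol 4.1.4, item 5.** Add that a participant may be escalated only after completing the 8 (±1)-week VTE DLT window at the starting dose. This costs one clause and a short delay to some dose increases. With enrolment ended it matters for participants still in the window and for any restart. The 4.1.3 counts and Table 8 do not change.
2. **Final analysis.** Check the exposure data for any dose increase inside the window. If there was one, keep the initial-dose column of SAP 5.2 and add a footnote to Table 3.22 and Listing 22. It should give the dose being taken at recorded onset and the date of the increase, and note that a scan-detected VTE may have begun before its recorded date. This uses the dosing dates and actual doses already planned for the exposure listing (SAP 8.1).
3. **Determinative period.** State in the SAP whether it includes the 8 (±1)-week VTE window, so that the contents of Table 3.22 and Listing 22 are clear. This takes one sentence.

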4.2. Scientific Rationale for Study Design

Given the high unmet medical need of relapsed/refractory advanced solid tumors and non-Hodgkin's lymphoma, this two-part Phase I study (207675) is proposed. This study evaluates the safety, tolerability, pharmacology, and preliminary clinical activity of GSK3368715. The study comprises a dose-escalation part to identify the MTD/

recommended expansion dose followed by two expansion cohorts to determine preliminary efficacy.

In Part 1, blood, serum and urine collections will be performed to characterize the pharmacokinetic and pharmacodynamic parameters of GSK3368715.

Cohort(s) of additional participants in Part 1, treated at or close to the expected MTD/RP2D, will be evaluated more extensively for metabolic and biomarker profiling. This cohort will provide samples for biomarker, pharmacodynamic, and metabolite assessment. Analysis of human samples will provide first-hand information on metabolism and disposition of GSK3368715 in humans. In addition to assessing known pharmacodynamic biomarkers, exploratory efforts will be conducted to evaluate the mechanism of action of GSK3368715, and discover novel pharmacodynamic and predictive biomarkers from blood, plasma, and tumor.

A subset of participants in Part 1, treated at or near the RP2D, will be evaluated more extensively to evaluate the effect of food on the pharmacokinetics of GSK3368715 (Section 4.1.1.1). This cohort will provide data that can be used to modify dosing instructions for participants in this and future studies (e.g., GSK3368715 may be taken without respect to food, or GSK3368715 must be taken on an empty stomach).

Once a RP2D dose of GSK3368715 has been identified that is safe, tolerable and demonstrates pharmacodynamic activity, enrolment into Part 2 may begin.

The intent of Part 2 is to evaluate MTAP as a potential selection biomarker in participants exposed to GSK3368715 at the RP2D. MTAP deficiency in tumor tissue will be evaluated as a potential biomarker to select participants for GSK3368715 study intervention and emerging data will be used to adaptively recruit participants based on MTAP status. to achieve approximately 50% of participants within each tumor type having an MTAP deletion.

